## **9.6 Data Management**

The main purpose of the eCRF is to obtain data required by the non-interventional study protocol in a complete, accurate, legible, and timely manner. The data in the eCRF should be consistent with the relevant source documents.

The investigator or designee is responsible for ensuring that the data collected in the course of this study is accurate and documented appropriately on all applicable forms. Data will then be processed, evaluated, and stored in pseudo-anonymous form in accordance with applicable data protection regulations. The investigator must ensure that the eCRFs and any other associated documents forwarded to Sponsor or its designated organization contain no mention of any patient names.

The data will be entered into a GCP Compliant and validated database. The Sponsor/Contract Research Organization (CRO) or its designee will be responsible for data processing, in accordance with the Sponsor's/CRO's data management procedures. Database lock will occur once quality control and quality assurance procedures and coding activities have been completed. PDF files of the eCRFs will be provided to the investigators at the completion of the study.

The eCRFs are essential study documents and must be suitable for regulatory inspections and submissions.

## 9.7

## Data Analysis

Further details will be provided in an integrated analysis plan (IAP). The IAP will be finalized prior to any planned analysis, but latest before database lock and will be included in the clinical study report for this protocol. The final IAP will consider any amendment to the protocol.

### 9.7.1

### Analysis Sets

#### Full Analysis Set

The Full Analysis Set (FAS) is defined as all enrolled patients who were treated with at least one course of treatment with cladribine tablets.

Additional analysis sets may be described in the IAP.

#### 9.7.1.1

#### Analysis Subgroups

The analysis of the primary and secondary outcomes will be performed among the following subgroups of the most recent DMT taken prior to initiation with cladribine tablets. A non-exhaustive list of such regulatory approved DMTs by subgroup is provided in [Table 2](#).

**Table 2** Subgroups by Most Recent prior disease-modifying therapy

Previous disease-modifying therapy class	Therapies
Naïve to disease-modifying therapies	-
Prior platform therapy	Interferon beta; teriflunomide; dimethyl fumarate; glatiramer acetate
Prior high-efficacy cell-depleting treatment	Alemtuzumab; ocrelizumab
Prior high-efficacy non-depleting treatment	Natalizumab; fingolimod

Patients will be classified in only one of the subgroups. For patients who have taken more than one prior DMT, the drug which was taken most recently prior to treatment initiation with cladribine tablets (i.e., the last prior DMT) will be used for categorisation. Patients who had a gap period between the most recent prior DMT and the initiation with cladribine tablets will be classified in the subgroup according to their last prior therapy.

The medications will be coded using WHO Drug Dictionary. A list of the medication codes that qualify for enrolment in each subgroup will be provided in the IAP.

### 9.7.2

### Derived and Transformed Data

Details on the eventual derivation/transformation of the analysis variables will be given in the IAP.

In general, no imputation of missing data will be done.

### 9.7.3 Statistical Methods

No formal statistical hypothesis will be tested, given the descriptive nature of the study.

Descriptive statistics will be used to summarize data. Quantitative (continuous) variables will be summarised using descriptive statistics, i.e., the number of patients with non-missing value, the number of patients with missing value, the mean, SD, median, minimum, and maximum, and first and third quartile. Qualitative (categorical) variables will be displayed as frequency counts and percentages (n, %).

If CIs are to be calculated, these will be 2-sided with a confidence probability of 95%, unless otherwise specified. For continuous data, CIs for the mean will be calculated assuming a normal distribution of the data. The CIs for binary outcomes will be presented using the Clopper-Pearson method.

The primary, secondary, and other analyses will be performed on the FAS.

#### Primary Outcome Analysis

The annualised relapse rate for a patient is defined as the number of clinician's confirmed relapses that occurred in the year prior to the date of cladribine tablet initiation, and in Years 1, 2, 3, 4 and 5 after treatment initiation with cladribine tablets (upon availability, depending on the available observation time):

- Year prior to date of cladribine tablet initiation: Month -12 to the day before the date of cladribine tablet initiation (Start Month 1)
- Year 1: Start Month 1 to End of Month 12
- Year 2: Start Month 13 to End of Month 24
- Year 3: Start Month 25 to End of Month 36
- Year 4: Start Month 37 to End of Month 48
- Year 5: Start Month 49 to End of Month 60

Relapses will be counted for the defined time period if the date of onset of the relapse is within the defined time period. In the analyses defined in the IAP, an "induction period" after treatment initiation may be considered for the annualised relapse rate in Year 1.

The annualised relapse rate for a patient will be calculated by dividing the number of clinician confirmed relapses during the period by the person-years of the patient (i.e., the period [in days] that a patient was observed in the study divided by 365.25).

The estimated annualised relapse rate in each of the defined years above will be summarised using descriptive statistics for continuous variables.

The annualised relapse rate will be described overall and among the subgroups by most recent prior DMT, as defined in [Table 2](#).

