Data Analysis	
The estimated annualised relapse rate in the year prior to treatment initiation with cladribine tablets, and in years 1, 2, 3, 4 and 5 (upon availability, depending on the available observation time) after initiation will be summarised using descriptive statistics for continuous variables.
 
The proportion of patients who remain relapse-free in each year (and up to 5 years) after initiation of treatment (among patients active at the start of each year) will be summarised using Kaplan-Meier summary statistics. The Kaplan-Meier survival curve for time from initiation to first relapse will be plotted.
 
Proportion of patients who discontinued cladribine tablets and reasons for discontinuation, proportion of patients with confirmed disability progression, and the subsequent DMTs (none or by DMT type) received after cladribine tablet treatment initiation will be summarised using descriptive statistics.
 
The incidence rates of AEs will be summarised by system organ class and preferred term using the Medical Dictionary for Regulatory Activities (MedDRA).

Milestones	Start of data collection: Q3 2021 End of data collection: Q3 2023 Final report of study results: Q2 2024
-------------------	--

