## 9 Research Methods

### 9.1 Study Design

#### 9.1.1 Design Overview

This will be a multicentre chart review, Phase IV study, to be conducted across approximately 7 or 8 sites in the UK, using medical records of patients who initiated cladribine tablet monotherapy for treatment of HDA-RRMS per clinical practice. The observational chart review study design, allowing collection of real-world data dating back to product launch, will maximise the patient observation periods while minimising the burden for the sites and patients.

Patients with HDA-RRMS who initiated treatment with cladribine tablets and are fulfilling the other study eligibility criteria will be identified from patient records and asked to consent to participate in the study. Informed consent may be obtained at the site or remotely (additional details are provided in [Section 10.1](#)). Patients should have initiated treatment with cladribine tablets between 22 August 2017 (i.e., date of EU marketing authorisation of cladribine tablets) and at least 3 years before enrolling into the study. In addition, the patient should have completed at least Year 1 of cladribine treatment (i.e., 2 treatment weeks). Sites should aim to enrol patients in chronological order, based on the start date of treatment with cladribine tablets: i.e., patients who initiated cladribine tablets first will be contacted for enrolment first and their data should be abstracted first.

In this observational chart review study, the drug was prescribed before the patient was enrolled in the study as part of routine clinical practice and independent from participation in the current study.

[figure not shown]
The enrolment date is defined as the date of signing informed consent. Annual chart reviews will be based upon the date of cladribine tablet initiation, which is defined as the start date of Year 1 treatment with cladribine tablets as documented in patients' medical records. This study will involve 2 chart abstractions, with the first chart abstraction at the patient's enrolment and the second chart abstraction approximately 1 year after enrolment ([Figure 1](#)).

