The first chart review will take place after obtaining patients' consent to participate in this study. Patient data will be abstracted within 28 days after obtaining informed consent. The data will be abstracted from the medical chart and will include relevant medical history, data recorded in the year prior to cladribine tablet initiation, and data recorded between the date of treatment initiation with cladribine tablets and the study enrolment date ([Table 1](#) and [Section 9.3](#)). In addition, the patient's general practitioner may be contacted by the principal investigator or a member of the site team to obtain information regarding medical history and concomitant medications.

The second chart review will be conducted approximately 1 year after enrolment (within a window of 14 days from a year after the enrolment date). This second chart abstraction will collect data recorded between the enrolment date and the date of the second data abstraction ([Table 1](#) and [Section 9.3](#)).

The data to be collected are routinely collected information per clinical practice, including demographic data, disease characteristics (relapse reports, Expanded Disease Severity Scale [EDSS] scores, MRIs, and lymphocyte counts, as available), treatments (cladribine tablets, other DMTs for MS, and COVID-19 vaccines), medical history, and selected AEs.

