#### **9.2.1.1                            Inclusion Criteria**

For inclusion in the study, all of the following inclusion criteria must be fulfilled:

1. At least 18 years of age at cladribine tablet treatment initiation
2. Physician diagnosis of HDA-RRMS as defined by clinical or radiological features
3. Treatment initiation with cladribine tablet monotherapy on or after 22 August 2017 and at least 3 years before enrolment
4. Completion of Year 1 treatment of cladribine tablets (Week 1 and Week 2 treatment, per recommended dose in Year 1: 1.75 mg/kg body weight, cumulatively)
5. Provide written informed consent to participate in the study

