## 9.2.3 Observation Period

The total observation period per patient will vary, depending on the pre-enrolment time on cladribine tablet treatment (i.e., the period between the date of cladribine tablet initiation and study enrolment date). The observation period per patient, counting from 1 year prior to cladribine tablet initiation until the date of the second chart review, will be at minimum 5 years and at maximum 7 years.

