- Number of tablets taken per week of ‘Year 1’, ‘Year 2’ and each subsequent course of cladribine
- Total number of tablets taken on ‘Year 1’, ‘Year 2’ and each subsequent course of cladribine
- Cumulative number of tablets taken (cumulative over Year 1 and Year 2, and cumulative over all courses of cladribine treatment)
- Number % of patients with no dose and dose delayed (with the corresponding reasons)
- Number % of patients with a complete course of cladribine at ‘Year 1’, ‘Year 2’, any additional courses of cladribine treatment and overall

14 Effectiveness

The following analyses will be performed based on the FAS by the most recent prior DMT and overall.

14.1 *Primary Outcome: ARR*

14.1.1 *Primary Objective: Derivation and analysis of the primary outcome: ARR*

The annualised relapse rate (ARR) will be derived from the 'Clinical Confirmed Relapses' CRF page.

The relapses observed will be assigned for the calculation for the ARR as indicated on [Table 1](#) in Section 9.6.

The ARR for a patient will be calculated by dividing the number of clinicians confirmed relapses observed within each period (Year) by the person-years of the patient in the period.

The person-years for a patient will be assigned as follows:

- $(365.25-84)/365.25$ years for time-point 'Year 1' for the full effectiveness period (main analysis)
- $(365.25-56)/365.25$ years for time-point 'Year 1' for the amplified effectiveness period (sensitivity analysis #1)
- 1 year for time-point 'Year 1' for the full treatment effectiveness period (sensitivity analysis #2)

And 1 year for each other interval (-1, 2, 3, 4, 5) unless the date of last contact occurs within that interval. In this case that interval person-years will be calculated until the date of last contact. The patient will not contribute to the ARR calculation for the following intervals (if any).

The 95% confidence interval (CI) will be calculated using the exact Poisson method.

14.2 *Secondary Outcomes*

14.2.1 *Secondary Objective: Derivation and analysis of the secondary outcome: RFR*

The relapse-free rate (RFR) is defined as the time from the on-treatment period start date (see [Table 3](#)) until the date of the first relapse or death as assessed by the investigator:

- RFR (years): $(\text{First relapse date or death or date of censoring} - \text{on-treatment start date} + 1) / 365.25$.

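### Year 5 ARR rests on a selected, partly observed subset and no ARR is planned in a common set of patients, so a Year 4 to Year 5 step can reflect who is observed

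*Protocol*

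**What the plan says.** Protocol 9.7.3 (Primary Outcome Analysis) defines ARR for the year before initiation and for Years 1 to 5, each "upon availability, depending on the available observation time". SAP 14.1.1 gives a patient one person-year per interval (less the induction period in Year 1). If last contact falls inside an interval, only the time up to that date counts. After that: "The patient will not contribute to the ARR calculation for the following intervals (if any").

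Four design rules decide who is observed in which year:

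- Eligibility (Protocol 9.2.1.1): "Treatment initiation with cladribine tablet monotherapy on or after 22 August 2017 and at least 3 years before enrolment".
- The second chart review (Protocol 9.1.1) is "within a window of 14 days from a year after the enrolment date".
- Total observation, counting one pre-treatment year (Protocol 9.2.3), "will be at minimum 5 years and at maximum 7 years".
- Calendar limits (Protocol Abstract): "Start of data collection: Q3 2021 End of data collection: Q3 2023".

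Enrolment order is an aim and not a requirement: "Sites should aim to enrol patients in chronological order" of treatment start (Protocol 9.1.1).

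For two secondary outcomes, the 5-year relapse-free proportion and the 5-year proportion with no other DMT, Protocol 9.7.3 limits the analysis to patients who have five years of observation. The primary outcome has no matching set. SAP section 7 records no changes to the planned analyses, and SAP 14.1.1 adds no ARR in a fixed group of patients.

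**The concern.** The primary objective is a yearly series to Year 5, and the protocol's rationale is medium- to long-term outcome. Readers will set the Year 5 figure beside Years 1 to 4 and ask whether the effect lasts. That comparison is sound only if the same patients stand behind both figures, or if those who reach Year 5 relapse at the same rate as those who do not.

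The design does not secure the first condition, and the documents give no information on the second. A rise or fall at Year 5 could then be read as waning or sustained effect when no patient's relapse rate has changed. The same applies within each prior-DMT subgroup, where numbers are smaller.

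**Working it through.** **1. The plan's own observation period.** Minimum: 1 pre-treatment year + 3 years to enrolment + 1 year to second review = 5 years. Maximum: 22 August 2017 to the end of collection, plus 1 year, is 6.9 years (to 1 July 2023) or 7.1 years (to 30 September 2023). The stated 5 to 7 years is reproduced, so follow-up after initiation is about 4 to 6 years.

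**2. Which years are scheduled for everyone.** The earliest permitted second review is 3 × 365.25 + 365 − 14 = 1,446.75 days after initiation. SAP Table 1 ends Year 4 on Day 1461, so a completer is at most about 14 days short of a full Year 4. Year 5 runs from Day 1462 to Day 1826 and is not guaranteed to anyone.

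**3. Who can have Year 5 time.** Assume the last review is on 30 September 2023.

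- Latest enrolment: 30 Sep 2023 − 351 days = 14 Oct 2022. Latest eligible initiation: 3 years earlier, 14 Oct 2019.
- Full Year 5: 30 Sep 2023 − 1,825 days = 1 Oct 2018.
- Any Year 5 time: 30 Sep 2023 − 1,461 days = 30 Sep 2019.

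Initiations after about 1 October 2018 therefore cannot supply a full Year 5, but many can supply part of one.

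**4. How much Year 5 time to expect.** The documents give no distribution of initiation or enrolment dates, so this is a simulation under assumptions. Initiations are uniform from 22 August 2017. Enrolment starts between 1 July and 30 September 2021 and ends on 30 September 2022. It takes place in initiation order, at random, or as soon as each patient is eligible. Review comes 365 days later, and a year up to 14 days short counts as full.

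| Initiations up to | Some Year 5 time | Full Year 5 | Year 5 person-years per patient |
|---|---|---|---|
| Sep 2019 | 41% to 100% | 0% to 31% | 0.18 to 0.55 |
| Sep 2018 | 77% to 100% | 0% to 100% | 0.33 to 1.00 |

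Year 4 gives 1.00 person-year per patient in every scenario. The planned break is between Year 4 and Year 5.

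**5. What composition alone can do.** Let f be the share reaching Year 5, r the ratio of their relapse rate to that of the others, and 0.14 the overall ARR (the expected value in Protocol 9.5). No patient's rate changes over time.

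- If those reaching Year 5 have the higher rate, Year 5 ARR = r × 0.14 / (f·r + 1 − f).
- If they have the lower rate, by the same factor, Year 5 ARR = 0.14 / (f + (1 − f)·r).

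| f | r | Year 5 if higher | Year 5 if lower |
|---|---|---|---|
| 0.5 | 1.5 | 0.168 | 0.112 |
| 0.5 | 2 | 0.187 | 0.093 |
| 0.3 | 2 | 0.215 | 0.082 |

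For example, 1.5 × 0.14 / 1.25 = 0.168. Earlier years would read 0.14 throughout. Both f and r are assumptions.

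**6. Precision.** Exact Poisson 95% intervals at ARR 0.14, for 90 patients: 0.074 to 0.241 on 90 person-years, 0.053 to 0.299 on 45, and 0.030 to 0.400 on 22.5. For 200 patients: 0.093 to 0.202 on 200 and 0.077 to 0.235 on 100.

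**7. Why membership needs the chart review date.** SAP 9.5 builds last contact from recorded events and assessments, including relapse dates. The chart review date is not in the list. A reviewed patient with a quiet chart can drop out of later years, while a relapse record extends last contact. A Year 5 cohort defined by last contact could therefore be selected on the outcome.

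**The case against.** The other side has real strengths.

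- The study is descriptive. It tests no hypothesis and plans no between-year contrast, so no error rate is affected. This stands, but a primary series reported to Year 5 invites the comparison, and wide intervals do not correct composition.
- The plan openly makes later years depend on availability, and Protocol 9.9 lists selection and attrition as limitations. It does so only in general terms and does not mention Year 5.
- The number of patients is already to be reported with continuous summaries (Protocol 9.7.3; SAP section 9), and ARR is already split by most recent prior DMT. Both help. Neither separates time since initiation from the initiation cohort.
- Enrolling in initiation order can narrow the gap. If recruitment stops at September 2018 initiations, follow-up under that order is about 4.9 to 5.1 years for all. The protocol permits later initiations, so this is not assured.
- A cohort with a full Year 5 may be small or even empty. That limits what can be said about durability, and it does not make the all-available comparison safer.

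Two stronger readings should be resisted. A reader might infer that the whole series, from the pre-treatment year to Year 5, rests on a changing set. By design it does not. Before Year 5 the set changes only through withdrawal or the last-contact rule. A reader might also infer that Year 5 contains only early initiators. That holds for a complete Year 5, but SAP 14.1.1 counts partial time, so initiators into 2019 can contribute.

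**Conclusion.** The point holds for the step from Year 4 to Year 5. Years −1 to 4 are scheduled for every completer. Year 5 depends on the interval from initiation to second review, is partly observed for many, and is compared with earlier years without any common-cohort analysis. The protocol already restricts two 5-year secondary proportions in this way, so the gap in the primary outcome is one of consistency as well as interpretation.

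No definite percentage can be attached to the distortion. Nothing in the documents says whether patients with longer follow-up relapse more or less often. The illustrated Year 5 values (0.168 to 0.187, or 0.112 to 0.093, against 0.14) rest on an assumed share of one half and assumed rate ratios of 1.5 to 2. The 1 October 2018 limit rests on an assumed last review on 30 September 2023. The single-year estimates remain valid descriptions of the patients observed in each year.

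**What to change.** Add to SAP 14.1.1:

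- A supplementary table of ARR for Year −1 and Years 1 to 5, overall and by prior DMT, in patients whose second chart review falls on or after Day 1826. Set membership by the chart review date, not by last contact in SAP 9.5, and give each member the full person-time of every interval (less the induction period in Year 1).
- Person-years beside every yearly ARR, in this table and the planned one.
- A rule that any statement on change from earlier years to Year 5 rests on this table. If the cohort is too small to be informative, the report should say that such change cannot be assessed.
- A sentence in the limitations on the composition of Year 5.

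Keep the all-available table as the main estimate for each year. A separate Year 4 cohort table is optional, because it would nearly duplicate the planned one.

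The cost is one table from data already held: SAP 10.1 already classifies patients by the timing of the second review. The downside is wide intervals, above all within prior-DMT subgroups.

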#### Secondary Outcome Analysis

The proportion of patients who remain relapse-free in each year after treatment initiation (among patients active at start of each year), at 4 years after treatment initiation and at 5 years after treatment initiation (among patients with 5 years observation time available), and the time from cladribine tablet initiation to first relapse will be described using Kaplan-Meier method. Kaplan-Meier survival curve will be plotted (overall and by most recent prior DMT subgroup) and a table with the probabilities of remaining relapse-free in each year after initiation of treatment will be produced.

The proportion of patients who discontinued cladribine tablets and reasons for discontinuation will be summarised using descriptive statistics.

Subsequent DMTs (none or by DMT type) received after treatment with cladribine tablets will be described up to 5 years after cladribine tablet initiation. The proportion of patients who did not receive any other DMT up to a total of 4 years and up to a total of 5 years (among patients with 5 years observation time available) after cladribine tablet treatment initiation will be analysed using descriptive statistics. Depending on the availability of data and the missing data pattern, a survival analysis may be performed to account for loss to follow-up patterns.

The annual EDSS scores at treatment initiation and start of cladribine tablet treatment at Year 2 will be summarised using descriptive statistics. The proportion of patients with disability progression confirmed over 6 months at 2 years after cladribine tablet initiation will be summarised using descriptive statistics.

The number and percentages of patients with AEs will be reported, and the number of AEs itself. The incidence rates of AEs will be summarised by system organ class and preferred term using the Medical Dictionary for Regulatory Activities (MedDRA). Additional summaries will be presented by severity. The AEs will be reported overall, and as stratified in the last prior MS DMT subgroups (as defined in [Table 2](#)).

CCI

